2	
Inclusion and Exclusion Criteria:
 
 Subjects that are unable to lie on their backs for long periods of time may experience discomfort. (Inclusion added) The goal of this study is to enroll subjects with mild to moderate disease; therefore the age minimum has been reduced to 35, as long as they do meet all other eligibility requirements. (Inclusion expanded) In Version 1, many subjects on anticoagulant use were excluded. Newer novel oral anticoagulants target different proteins as opposed to warfarin, and act for a shorter period of time reducing the risk of bleeds. Therefore, the exclusion was clarified to only exclude those on warfarin, or those with a PT-INR >2.5 or those who have and need routine INR or PTT testing. (Exclusion clarification) 
Analysis Methods:
 
 The analysis methods for the predicate and investigational devices have been adjusted to employ the same steps to process and analyze the respective collected PPG data In Version 1, human-in-the-loop analysis was employed for the predicate device which required subjective placement of points. Incorporation of the same analysis steps as the investigational device removes any potential human bias in the analysis and instead employs a consistent, fixed algorithmic analysis 	[name], CEO

INVESTIGATOR STATEMENT OF COMPLIANCE

The trial will be carried out in accordance with International Conference on Harmonisation Good Clinical Practice (ICH E6(R2)), United States (US) Code of Federal Regulations (CFR) applicable to medical device clinical studies (21 CFR Part 50, 21 CFR Part 56, the abbreviated IDE requirements of 21 CFR Part 812), and ISO 14155:2020, *Clinical investigation of medical devices for human subjects – Good clinical practice*.

I agree, as an Investigator conducting this study, to the following:

1 PROTOCOL SUMMARY

1.1 SYNOPSIS (BRIEF)

Title:	Wave Crossover ECP Study for Simplified Therapy
Short Title:	WaveCRESST
Sponsor:	Pression, LLC
Investigational Device Type:	External Counter-Pulsation (ECP)
Investigational Device Name:	Pression Wave PRO External Counter-pulsation System
Control Predicate Device:	Applied Cardiac Systems (ACS) NCP-2 External Counter-Pulsation System
Intended Use/Indication(s) for Use:	
The Pression Wave PRO External Counter-Pulsation System is indicated for the treatment of chronic stable angina (CSA) that is refractory to optimal anti-anginal medical therapy and without options for revascularization. In addition, it is intended for use in healthy patients to provide improvement in vasodilation, increased VO₂, and increased blood flow.
 
It is intended for use under the oversight of a healthcare professional.

Device Description (Brief):	The Pression Wave PRO External Counter-Pulsation System applies compression to the calves, timed to ventricular diastole, with the aim of increasing blood flow towards the coronary arteries when the heart is relaxed, thereby increasing cardiac perfusion.
Clinical Background (Brief):	
 Ten human volunteer studies were conducted with the predecessor technology to the Wave PRO System that support the safety and effectiveness of the Wave device. A combined total of 150 healthy volunteers ranging from 18-85 years of age were studied. In all previous studies, the primary effectiveness endpoints were related to increasing athletic performance. 
 There were no reported adverse events in any of the studies. Furthermore, the studies identified that patients found the pressure applied to the calves of up to 100 mmHg comfortable. Recent research on the Wave PRO System found that individuals easily tolerated pressure up to 300 mmHg. The most recent volunteer pilot study for the Wave PRO System itself involved seven age-appropriate participants in a head-to-head comparison with the ACS NCP-2 (predicate ECP device). The Wave PRO device produced the intended hemodynamic effects with no adverse events.
Purpose of Study:	The purpose of this study is to demonstrate substantial equivalence between Pression's Wave PRO System and a commercially available predicate ECP device to support a U.S. 510(k) Premarket Notification for the Wave PRO System.

Study Objectives:	The study objective is to demonstrate substantial equivalence (non-inferiority) of the hemodynamic effect between the Wave PRO System and the predicate ECP device (ACS NCP-2) as measured by the diastolic augmentation (DA) ratio and systolic unloading.
Study Design:	
Participants will receive compressions from both ECP systems, one system at a time, in random order. Diastolic augmentation ratio will be evaluated for each participant on each test ECP system.
 
Participants will be aged 35+, with a history of mild to moderate coronary artery disease, serve as their own control, and meet the Inclusion Criteria and none of the Exclusion Criteria.
 
Total participant time is approximately 2.5 – 3 hours.
 
Data to be collected includes pulse photoplethysmography (PPG) and vital sign information. Demographic data and a device-related questionnaire will be collected.
 
Data Analysis will include calculating the average DA ratio for each ECP system from the pulse waveforms collected, for each participant. Systolic unloading level will be recorded for Wave PRO.

Number of Participants:	The required sample size is 44 participants with paired DA ratio data. Allowing up to 12% attrition , approximately 50 participants will be randomized to the ECP device order.
Number and Location of Investigational Sites:	One study site in the United States.
Expected Study Duration:	
Recruitment: 6 Weeks
 
Participant Follow-up: Phone call 1 day after the ECP session
 
Total Study Duration: 10 Weeks

Randomization:	The order in which the participant will receive the two ECP sessions will be randomized.
Safety Endpoint 1:	Occurrence of device-related Serious Adverse Events (SAEs).
Safety Endpoint 2:	
Rate of device-related Adverse Events (AEs).
 
Follow up questionnaire to address bruising, abrasion, soreness.

Primary Performance and/or Effectiveness Endpoint:	The average DA ratio for each ECP session, calculated from the eighth minute of compressions for each participant.
Secondary Performance and/or Effectiveness Endpoint(s):	
 The level of systolic unloading for the Wave PRO based on the systolic peaks during compressions compared to baseline of the PPG data, captured using the independent data acquisition system. Number of participants that complete 10 mins of each of the ECP devices (Wave PRO and predicate ECP device) Participant comfort level with the Wave PRO and predicate ECP device, assessed at the conclusion of each ECP session

	
 • Time to set up a participant (i.e., sleeved up and sensors attached) and ready to start treatment • Participant preference for one of the two ECP systems (assuming 35 hours for a full course of ECP)
Key Inclusion Criteria:	
 ○ Age 35 years or greater ○ History of mild to moderate coronary artery disease (CAD) ○ Able to ambulate without assistance ○ Able to lay down (approximately 5 degree angle) for the duration of the protocol required procedures ○ Able and willing to give informed consent ○ Able and willing to participate in the clinical study and complete all questionnaires provided
Key Exclusion Criteria:	
 ○ Unstable angina within prior 3 months ○ Canadian Cardiovascular Society (CCS) Class III or IV Angina ○ Moderate to severe peripheral arterial disease (PAD) ○ Myocardial infarction in the past 3 months ○ Coronary artery bypass grafting (CABG) in the past 3 months ○ Any major surgery within the past 3 months ○ Decompensated heart failure ○ Cardiac catheterization or arterial femoral puncture in the past 2 weeks ○ Presence of mechanical circulatory support (MCS) device ○ Pacemaker or other implantable pulse generating device ○ Valve disease, including aortic insufficiency ○ Abdominal or thoracic aortic dissection or aortic/cerebral aneurysms requiring clinical intervention ○ Severe pulmonary disease ○ Bleeding diathesis ○ Patients undergoing warfarin anti-coagulation therapy, or with PT-INR > 2.5, or who have routine INR or prothrombin time tests ○ Active thrombophlebitis ○ Uncontrolled hypertension (greater than 180/110 mmHg) ○ Baseline heart rate >120 BPM or <40 BPM ○ Arrhythmia and/or abnormal heart rhythm ○ Major hand injuries or amputation that would interfere with finger PPG ○ Unhealed wounds/fractures below the waist or lower limb amputation, major lower body musculoskeletal injuries ○ Lower body vascular stents (arterial/venous) ○ Currently undergoing ECP treatment ○ Pregnancy ○ Currently participating in any other clinical study of an investigational device or drug where treatment has not yet been completed ○ Any medical condition that, in the opinion of the principal investigator (PI), would present undue risk to the participant

Key Data to be Collected:	Baseline Data: 
 • Demographics: age, sex, race, ethnicity • Relevant medical history and vital statistics Hemodynamic Measurements During ECP: 
 • PPG: Flow and heart rate • EKG (aka. ECG): Heart rhythm Follow-up and Safety: 
 • Participant Survey • Safety/AE Assessment
Statistical Analysis:	
Assuming a true difference in DA Ratio of 0 with standard deviation of 0.30 for Wave PRO – predicate ECP, a sample size of 44 participants is adequately powered with at least 90% power with a 1-sided alpha of 0.025 to test non-inferiority of Wave PRO vs predicate with a margin of –0.15. Factoring in 12% attrition, approximately 50 participants will be randomized.
 
Primary effectiveness: An analysis of variance (ANOVA) model for crossover design will be performed and the pairwise difference between two treatments DA ratios (Wave PRO – predicate ECP) in the treatment least square mean and its 95% CI will be constructed. If the lower bound of this 95% confidence interval is greater than -0.15, then the null hypothesis will be rejected, concluding that Wave PRO is not inferior to the predicate ECP. A p-value will be constructed using the LS means parameter estimates and standard error to test the hypothesis.
 
Descriptive statistics will be used to summarize all other secondary endpoints.

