2.3 RISK/BENEFIT ASSESSMENT

2.3.1 KNOWN POTENTIAL RISKS

PRESSION completed a hazard analysis/risk assessment through design failure modes and effects analysis (DFMEA), classifying risk based on severity of harm and anticipated occurrence with the Wave PRO ECP system, in accordance with ISO 14971. As PRession has mitigated almost all risks of the Wave PRO device, only the residual clinical risks are discussed here.

The risk analysis identifies that the participant may experience minor abrasions, bruising and/or calf muscle soreness/tenderness from the pressure application during compression. Both abrasions and bruising can be minimized by using an interfacing layer, such as a tight-fitting knee-high sock or sleeve, between the participant’s skin and the compression sleeve of the Wave PRO. Calf muscle soreness/tenderness as a result of normal compressions during system operation is expected to resolve without medical intervention.

Known side effects for existing ECP systems on the market, including the predicate ACS NCP-2 device, include skin abrasion, bruising, muscle ache, blistering, and paresthesia (prickling sensation), all of which are also potential side effects of the Wave PRO ECP system. Side effects of ECP treatment are generally well tolerated and can be minimized with additional padding at the interface of the compression cuffs and the participant. Other side effects can be resolved with the application of topical creams.

Rare side effects of ECP may include skin breakdown and increase in adverse cardiac events.

Any discomfort during an ECP session will be recorded for each participant, along with any adverse events during testing.

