8.3 SAFETY AND OTHER ASSESSMENTS

Adverse Events/Serious Adverse Events (SAEs) will be recorded on the Adverse Event eCRF from the time the participant signs Informed Consent until study exit. The Investigator and any qualified designees are responsible for detecting, documenting, and recording events that meet the definition of an AE or SAE in the AE eCRF and remain responsible for following up all AEs.

The participant will be asked to complete surveys after each ECP device session and again one day after completion of the study procedures.

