9.3.2 SAFETY ENDPOINTS**Safety Endpoint 1:**

Occurrence of device-related Serious Adverse Events (SAEs) as reported on the case report forms.

Analysis cohort: Safety cohort.

Analysis methods:

The number of events, number of participants and proportion of participants experiencing any device-related SAE will be summarized by treatment arm. There are no hypothesis tests, but 95% CI for the proportion of participants with an event may be calculated.

Safety Endpoint 2:

Rate of device-related Adverse Events (AEs) as reported on the case report forms.

Analysis cohort: Safety cohort.

Analysis methods:

The number of events, number of participants and proportion of participants experiencing any device-related AE (including serious) will be summarized by treatment arm. There are no hypothesis tests, but 95% CI for the proportion of participants with an event may be calculated.

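### The follow-up questionnaire's stated content is narrower than the protocol's own list of ECP effects, so known effects may be captured unevenly

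*Combined protocol and SAP*

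**What the plan says.** The synopsis (Section 1.1) defines Safety Endpoint 2 as the rate of device-related adverse events and adds one line on the questionnaire: "Follow up questionnaire to address bruising, abrasion, soreness".

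Section 2.3.1 has three layers of risk. The sponsor's own risk analysis for Wave PRO finds that "the participant may experience minor abrasions, bruising and/or calf muscle soreness/tenderness from the pressure application during compression". For marketed ECP systems, including the predicate, the section lists abrasion, bruising and muscle ache, followed by "blistering, and paresthesia (prickling sensation), all of which are also potential side effects of the Wave PRO ECP system". It then adds: "Rare side effects of ECP may include skin breakdown and increase in adverse cardiac events".

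Adverse event collection is described elsewhere. Section 9.3.2 takes the endpoint from the forms: "Rate of device-related Adverse Events (AEs) as reported on the case report forms". Under Section 8.3, AEs and SAEs "will be recorded on the Adverse Event eCRF from the time the participant signs Informed Consent until study exit", and the investigator and designees "are responsible for detecting, documenting, and recording events that meet the definition of an AE or SAE in the AE eCRF". Section 8.4.1 defines an adverse event openly, without a closed list. The schedule in Section 1.2 has a Safety Assessment row, separate from the Participant Questionnaire row, at both the procedure visit and follow-up. Section 8.3 calls for surveys after each device session and again a day later. Under Section 4.3 the participant exits once the next-day call and questionnaire are done.

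**The concern.** Effects that participants are asked about tend to be reported more fully than effects they must bring up themselves. If the questionnaire follows the synopsis line, three effects are prompted and four others that the protocol itself names are not. The resulting safety profile could then partly reflect the form: prompted effects would look more frequent, and unprompted ones rarer or absent.

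This matters because the study supports a 510(k) submission and Section 9.3.2 summarizes device-related events by treatment arm. The prior experience in the synopsis is 150 healthy volunteers on predecessor technology and a seven-participant pilot, whereas this trial enrols people with coronary artery disease. The next-day call is the last planned contact, so a late, non-serious effect that is neither asked about nor mentioned then may not be recorded.

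**Working it through.** **Step 1. The lists side by side** (soreness is counted as the same effect as muscle ache).

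| Effect in Section 2.3.1 | How it is listed there | In the sponsor's Wave PRO residual risks | In the synopsis questionnaire line |
|---|---|---|---|
| Abrasion | known | yes | yes |
| Bruising | known | yes | yes |
| Muscle ache / soreness | known | yes | yes |
| Blistering | known | no | no |
| Paresthesia | known | no | no |
| Skin breakdown | rare | no | no |
| Adverse cardiac events | rare | no | no |

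The questionnaire line matches the residual-risk list exactly. It names 3 of the 5 known effects and neither of the 2 rare ones, so 4 of 7 are not named. This count describes one synopsis line, not everything the study captures.

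**Step 2. Other routes for the four effects.**
- During sessions: Section 2.3.1 has any discomfort and any adverse event in testing recorded. This does not reach later onset.
- End of session (Sections 6.1.2 and 6.2.2): blood pressure, heart rate and a questionnaire, then removal of equipment. No skin check is listed, and the questionnaire items are not given.
- Observation: about 10 minutes after the second session.
- Next day: a phone call with a questionnaire and a safety assessment. No section says what the safety assessment asks.
- Transfer: Section 10.1.7.2 has research staff enter the surveys. No section says that a positive answer is assessed as an adverse event, even for the three named effects.

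The routes exist, but none is described as a structured prompt for the four effects after the visit.

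**Step 3. What uneven capture could do.** The documents give no adverse event rate and no capture probability, so no under-count can be derived. The figures below are an illustration on assumed values.

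The denominator follows the plan: 44 / (1 − 0.12) = 50 randomized, taken as all treated. Let p be the assumed true participant-level rate and s the assumed share recorded.

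Expected recorded cases = 50 × p × s. Chance of recording at least one = 1 − (1 − p·s)^50.

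| p | s | Expected recorded | P(at least one) |
|---|---|---|---|
| 5% | 1.00 | 2.5 | 0.92 |
| 5% | 0.50 | 1.25 | 0.72 |
| 5% | 0.25 | 0.62 | 0.47 |
| 2% | 1.00 | 1.0 | 0.64 |
| 2% | 0.50 | 0.5 | 0.40 |
| 2% | 0.25 | 0.25 | 0.22 |

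**Step 4. Reading a reported zero.** With 0 of 50 recorded, the exact two-sided 95% upper limit is 1 − 0.025^(1/50) = 0.071. That limit applies to the recorded rate. If only half of cases are recorded, the limit on the true rate is 0.071 / 0.5 = 0.142. With s = 1 the limit stays at 0.071 and nothing is lost. The plan does not let a reader tell which applies.

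**The case against.** The strongest reply is that the endpoint does not come from the questionnaire. It comes from the case report forms, under an open definition of adverse event, with responsibility for detection placed on the investigator. There is in-session recording, a separate safety assessment at follow-up, and a Medical Monitor who evaluates events (Section 10.1.4). The questionnaire line is one sentence in a brief synopsis, the form is not in the documents, and its three items are those that the sponsor's risk analysis identified for Wave PRO. All of this stands.

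It rules out two stronger readings. A reader might infer that the questionnaire asks about three effects only and that the adverse event rate therefore under-counts known harms. The text does not say only, the form cannot be inspected, and complete capture through the adverse event form would leave no under-count. A reader might also infer that the protocol lists cardiac symptoms as ECP effects that go unasked. Section 2.3.1 speaks of a rise in adverse cardiac events, and serious ones would come through SAE reporting to the sponsor within 24 hours (Section 8.4.5).

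The reply does not supply the content of the follow-up safety assessment or the link from a questionnaire answer to the adverse event form. Open reporting makes capture possible; it does not make it even across effects.

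**Conclusion.** The point holds as a minor design improvement. The stated questionnaire content is narrower than the protocol's own list of effects, by 4 of 7, and no structured prompt for those four is described at the last contact. Capture may therefore be uneven, and a zero for blistering or paresthesia would be ambiguous. An under-count is possible but not demonstrated, and its size is unknown; the rates and capture shares above are assumptions.

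The conclusion rests on the synopsis line being a fair summary of the form, and on the safety assessment having no structured prompts beyond those described. If the form or the safety assessment already covers the four effects, only the wording of the protocol needs changing. The cardiac item is the weakest part, because it concerns non-serious complaints after the visit. The safety endpoints are descriptive with no hypothesis test, so the primary endpoint, power and alpha are unaffected.

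**What to change.** In the synopsis entry for Safety Endpoint 2 and on the questionnaire itself, extend the items to every effect named in Section 2.3.1: abrasion, bruising, muscle soreness or ache, blistering, paresthesia, skin breakdown, and any new cardiac complaint since the session. Use the same items after each device session and at the next-day call. The answers after the first session are the only ones that follow exposure to one device alone.

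In Section 8.3, state that any positive answer goes to the investigator for adverse event assessment and, where it qualifies, entry on the adverse event eCRF.

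The cost is a few yes/no items on an existing form, about one more minute per questionnaire, and IRB approval of the wording. The reported adverse event count may rise slightly.

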1.2 SCHEDULE OF ACTIVITIES (SOA)

Study Assessment/Procedure Time Frame, Days (Window)	Pre-Screen (-14 to 0)	Baseline Procedure (0)	Follow-Up (+1 to +3)
Phone Screen/Eligibility Determination ¹	X	X	
Participant Orientation Material	X	X	
Informed Consent		X	
Eligibility Review		X	
Data Collection (Medical History, Medications, Etc.)	X	X	
Presenting Vitals and Limited Physical Exam		X	
PRESSION Wave PRO Procedure ² and associated Data Collection		X	
ACS NCP-2 Procedure ² and associated Data Collection		X	
Participant Questionnaire		X	X
Safety Assessment		X	X
Phone Call			X
Study Exit			X

¹ Phone screen to assess potential eligibility may be performed with IRB approved phone script; Eligibility to be confirmed at the time of Baseline Procedure Visit.

² To be performed in random order.

2 INTRODUCTION

2.1 STUDY RATIONALE

The purpose of this study is to demonstrate substantial equivalence between Pression's Wave PRO External Counter-pulsation (ECP) System and a commercially available predicate ECP device to support a U.S. 510(k) Premarket Notification for the Wave PRO System.

Existing ECP systems are based on technology originating from the 1980s. As a result, current ECP systems are large, heavy, loud, and require constant input from a dedicated clinical operator. Pression's Wave PRO system is significantly lighter, easily moved and incorporates automation features that support accurate treatment delivery in terms of pneumatic inflation and deflation, without the need for a dedicated operator.

In accordance with prior FDA feedback, the study objective is to demonstrate substantial equivalence (non-inferiority) of the hemodynamic effect between the Wave PRO System and the predicate ECP device as measured by the diastolic augmentation (DA) ratio and secondary endpoints, including levels of systolic unloading.

2.2 BACKGROUND

External counter-pulsation (ECP) is a non-invasive circulatory enhancement treatment currently cleared for Chronic Stable Angina (CSA). Per FDA's 2013 re-classification of ECP devices, ECP is classified as "Class II (special controls) when the device is intended for the treatment of chronic stable angina that is refractory to optimal antianginal medical therapy and without options for revascularization." ECP enhances circulation by applying compressions to the lower limbs timed to the cardiac cycle.

Current ECP systems are large, loud, expensive, are only accessible in clinics, and must be operated by dedicated staff. Compressions in commercially available ECP systems are applied to the entire leg and buttocks and are timed to the patient's EKG. Treatment effectiveness is measured using a pulse photoplethysmography (PPG) finger sensor. A typical treatment course is a 1-hour session in a dedicated clinical facility five times per week for seven weeks (35 total sessions).

The Wave PRO ECP system consists of calf-worn sleeves which contain five pneumatically-inflated bladders that peristaltically compress the calf muscles distally to proximally towards the heart. This compression generates retrograde arterial flow back to the heart, thus augmenting coronary flow during ventricular diastole. Unlike existing systems, Pression's technology uses PPG for both detection and to measure treatment effectiveness, enabling direct hemodynamic feedback of the treatment.

Prior in-house testing data collected using the Wave PRO system demonstrated that Pression's underlying compression technology and algorithm worked in synchrony with the cardiac cycle to

enhance early-diastolic velocities, measured by ultrasonography at the abdominal aorta. This translates to improved perfusion of the coronary arteries during ventricular diastole. Prior studies related to athletic performance and recovery (combined total of 150 healthy participants) using the predecessor technology to the Wave PRO demonstrated that compressions increased retrograde arterial flow, mean arterial pressure and cardiac output, arterial blood flow to the heart and brain, and vascular conductance with no reported adverse events in any of the studies.

In accordance with ECP literature and available instructions for use, this study will measure the Diastolic Augmentation (DA) ratio, also referred to as Diastolic/Systolic (D/S) ratio and Effectiveness Ratio (ER), which noninvasively characterizes the hemodynamic effect and thus the clinical effectiveness of ECP treatment. DA ratio is a unitless measure which is “calculated as the ratio of the peak diastolic amplitude divided by the peak systolic amplitude”¹. In a typical, non-augmented, cardiac cycle, the diastolic peak is seen as a small increase in the arterial waveform just after the aortic valve closes (dicrotic notch). With augmentation, the peak diastolic amplitude is distinctly elevated and may reach a significant proportion of the peak systolic amplitude or in some cases exceed it. “In general, [ECP] therapists attempt to obtain the maximum DA [ratio] obtainable by finger [PPG]”².

